8.2 Secondary Outcome Measures

1) Secondary HIV outcomes:

- a. VACS Index. Change in VACS Index at 24 weeks compared with randomization. (score; derived from screening and week 24 laboratory and demographic data).
- b. CD4 Count. Change in CD4 count at 24 weeks compared with randomization (count; laboratory assay).

2) Engagement in HIV Care:

- a. ART Prescribed. Proportion of participants prescribed ART within 24 weeks following randomization (binary; medical record abstraction).
- b. ART Adherence. Proportion of participants taking 100% of prescribed ART doses in the past month at 24 weeks for those prescribed ART at any point during the 24 week trial (binary; self-reported VAS medication adherence measure).
- c. Retention in HIV Care. Proportion of participants with at least 1 HIV primary care visit in the past 12 weeks, measured at week 24 (binary; medical record abstraction).
- d. HIV Risk Behaviors. Past 30 day injection drug use, unprotected sex, multiple sexual partners as measured by the RAB at week 24 (binary; self-report).
- e. Quality of life. Past 30 day health-related quality of life as measured by EQ-5D at week 24, compared to baseline.

3) ART Adherence Mediation Variables:

- a. Days of Opioid Use. Number of days of opioid use since baseline, as measured by Timeline Follow Back (TLFB) at 24 weeks (count; self-report).
- b. Opioid Abstinence. Past 30 day opioid abstinence (by Addiction Severity Index (ASI)-lite self-report, Time-Line Follow-Back (TLFB) and urine drug screen (UDS) confirmation) in the final 30 days of the 24 week trial (binary; self-report + UDS).

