14.3 Timeline Follow Back (TLFB)

Timeline Follow Back (TLFB) assesses self-reported drug and alcohol use over the past 30 days, with high test-retest reliability and validity [155, 156]. Participants will be asked to report daily drug and alcohol use in the specified timeframe (e.g., since the last visit). TLFB will be completed at the following visits: baseline, treatment initiation, and weeks 4, 8, 12, 16, 20, and 24 (or the end of study visit, if not week 24) for assessment of secondary outcomes. Baseline TLFB assesses use in the 30 days prior to informed consent through to the date of the baseline visit.

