- a. **Days of Opioid Use** Number of days of opioid use between baseline and 24 weeks, measured by TLFB (count; self-report), will be used to compare opioid use by treatment group. Confirmatory analysis will assess opioid use by the number of days of opioid use in the last 30 days of the study (by ASI-lite; count; self-report) and the number of monthly urine drug screen (UDS) negative for opioids between baseline and 24 weeks (count; laboratory data). *Analyzed using rank-based methods such as Wilcoxon rank-sum tests.*
- b. **Opioid Abstinence** Past 30 day opioid abstinence (by Addiction Severity Index (ASI)-lite self-report, Time-Line Follow-Back (TLFB) and urine drug screen (UDS) confirmation) in the final 30 days of the 24 week trial (binary; self-report + UDS).

Analyzed via rank-based methods such as Wilcoxon rank-sum tests. Covariates can be considered via the cumulative logit model.

Mediation Analysis

Mediation will be tested using structural equation modeling with Mplus 7.3. These models estimate the effect of the intervention on the potential mediator (path a, e.g., the effect of intervention on *substance use*) and the effect of the mediator on the outcome or next proximal intermediate outcome (path b, e.g., the effect of *substance use* on *HIV medication adherence*). Longer mediation pathways can also be tested (e.g., a^*b^*c), and therefore the entire mediational path depicted in section 1.2.1 can be assessed in this framework. There is significant mediation if the product of these two paths (a^*b) is greater than zero (or the product of more pathways in a longer mediational chain). Statistical significance will be assessed using bias-corrected bootstrap confidence intervals on the product terms [171]. This test is by far the most powerful test of mediation [172] and can test multiple mediating pathways within a single structural model. Using the tables in Fritz and MacKinnon [171], we should have over 80% power for mediation when the standardized path coefficients (a and b) are .164, which corresponds to approximately 2.7% shared variance between the outcome and predictor variable (e.g., treatment and substance for the a-path in the example given above.) We will also examine whether there are differences in strength of mediational pathways across the opioid and alcohol disorder subgroups.

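### Outcome 3a is a raw count of TLFB opioid-use days with no denominator and no rule for partial records, so the comparison is open to bias if attendance differs by arm

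*Combined protocol and SAP*

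**What the plan says.** Section 17.9 (3a) sets out the main opioid-use comparison: "Number of days of opioid use between baseline and 24 weeks, measured by TLFB (count; self-report), will be used to compare opioid use". It gives the test as "Analyzed using rank-based methods such as Wilcoxon rank-sum tests". Section 8.2 words the variable slightly differently: "Number of days of opioid use since baseline, as measured by Timeline Follow Back (TLFB) at 24 weeks (count; self-report"; Sections 5.2 and 17.3 likewise place the measurement at 24 weeks.

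On collection, Section 14.3 says "TLFB will be completed at the following visits: baseline, treatment initiation, and weeks 4, 8, 12, 16, 20, and 24", or at the end-of-study visit if that is not week 24. It describes the look-back in two ways: TLFB "assesses self-reported drug and alcohol use over the past 30 days", and "Participants will be asked to report daily drug and alcohol use in the specified timeframe (e.g., since the last visit").

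Section 17.9 adds two confirmatory measures: ASI-Lite use days in the last 30 days, and "the number of monthly urine drug screen (UDS) negative for opioids between baseline and 24 weeks". Outcome 3b is abstinence in the final 30 days. Section 17.9.1 allows Poisson, zero-inflated and negative binomial models but names no exposure term. The missing-data rules (Sections 9.2.3.3, 17.2 and 17.10) concern viral suppression only.

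Sections 2.1, 5.2 and 6.1 make opioid-use days the mediator of ART adherence, so the variable serves a stated secondary aim.

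**The concern.** A count of events over follow-up needs a statement of how much follow-up it covers. None is given, so the score mixes how much a person used with how long that person kept attending. The plan allows two readings.

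- **Summed.** Reported days are added up. Days never assessed contribute nothing and so act as days without use.
- **Completers.** A participant without a week-24 TLFB has no value and is left out.

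The first confuses early departure with low use. The second is safe only if leaving is unrelated to use, and Section 17.2 itself argues that in trials of substance-using people missing data probably signal poor status.

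Differential attendance is plausible. The trial is unblinded (9.7), and only the XR-NTX arm must go through detoxification and induction (9.2.3.1). At stake are the between-arm opioid comparison and path a (treatment to opioid use) of the mediation model. An unstated rule also leaves the choice open until data are seen.

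**Working it through.** **The plan's own figure.** The only stated power that involves this variable is for mediation: over 80% at a = b = 0.164. Shared variance is 0.164² = 0.0269, or 2.7%, as stated. With N = 350 (assumed, as that sentence gives no N) and continuous normal variables, simulated bias-corrected bootstrap power is 0.82, so the figure is reproduced. It presumes that everyone has a mediator value. If 20% had none, N = 350 × 0.8 = 280 and the simulated power is about 0.72.

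**Ranking under the summed reading.** Six 28-day windows give 168 days.

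- Uses 20 of 28 days, leaves after week 8: 20/28 × 56 = 40 days.
- Uses 8 of 28 days, completes: 8/28 × 168 = 48 days.

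The heavier user ranks better.

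**Expected count when dropout is unrelated to use.** Assume a proportion d leaves permanently after 0 to 5 windows, uniformly (mean 2.5 of 6). At the pilot XR-NTX follow-up rate of 13/30 (Section 4.3), the expected count is 13/30 × 168 × (1 − d + d × 2.5/6).

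- d = 0: 72.8
- d = 20%: 64.3
- d = 40%: 55.8

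**False positives with equal true use.** The set-up is 175 per arm, use probability Beta(1, 1.5) in both arms (mean 40% of days), dropout weighted by exp(2p) so that heavier users leave more often, departure after 28, 56, 84 or 112 days, and a two-sided rank-sum test at 0.05. All dropout rates are assumptions.

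| Dropout, one arm vs other | Summed count | Completers only | Percent of assessed days |
|---|---|---|---|
| 25% vs 15% | 22% | 11% | 5–6% |
| 30% vs 15% | 37% | 19% | 5–6% |
| 40% vs 15% | 75% | 50% | 5–6% |

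Repeat runs gave 20–22%, 35–41% and 73–77% for the summed count. The errors favor the arm with more dropout. The apparent difference is about 5.3 days (summed) or 3.8 days (completers) at 25% vs 15%, and 13.3 or 11.6 days at 40% vs 15%.

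**If dropout is unrelated to use.** With 20% in one arm against 20%, 30%, 40% or 50% in the other, summed counts give 5%, 13%, 41% and 74%. Completers give 5–6% and percent of assessed days 4–5%.

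**If a true difference exists.** Take the pilot follow-up rates, 13/30 for XR-NTX and 10/30 for TAU. Without dropout the gap is 72.8 − 56.0 = 16.8 days, and power to detect the lower use on TAU is 93%. With dropout of 40% vs 20%, the gap in summed days is about 6.4 and power about 22%. Percent of assessed days keeps about 90%. The sign does not change.

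**Limits of the alternative.** The 5–6% above relies on each person's use being constant. Pilot use fell over time (19 to 10 and 18 to 13 days). With declining use equal in both arms and 40% vs 15% dropout, percent of assessed days gave 9–11%, and 18% with a steeper fall (20 to 8 days per 30). The error then runs against the arm with more dropout, because leavers contribute only the early, heavier period.

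**Look-back.** Visits are about 28 days apart. After one missed visit, a 30-day window covers 30 of 56 days and loses 26; a window since the last completed TLFB loses none.

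**The case against.** The plan does not say that unassessed days count as zero. A reader might infer this from the word count, but the wording of Sections 5.2, 8.2 and 17.3 equally permits treating participants without week 24 as missing. That stands: the summed score is one reading. It does not rescue the plan, because the completer reading is unbiased only if leaving is unrelated to use.

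The planned set is also wider than 3a. ASI-Lite days and outcome 3b use a fixed final window, so truncated follow-up cannot lower them, and the negative-urine count falls with absence, so it leans the other way. Together they might expose an artefact. However, ASI-Lite follow-up comes only from week 24 or an end-of-study visit (14.2), 3b likewise needs final-period data, and no rule says what to conclude if the measures disagree.

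A reader might also assume that failed XR-NTX induction means dropout. The documents do not support that: participants are followed regardless of treatment (9.6), may start XR-NTX until week 20 (9.1.9), and on withdrawal are asked to attend an end-of-study visit (23.9). The pilot's 5 of 12 starting XR-NTX within 4 weeks describes initiation, not retention in the study.

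Nor does 3a contradict the primary missing-data rule, which covers viral suppression only. The difference is one of direction, and only under the summed reading. Harm to path b is limited too: ART adherence is self-reported for the past month at 24 weeks, so most leavers lack that outcome.

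**Conclusion.** The concern holds in conditional form. Outcome 3a has no denominator and no rule for partial TLFB, and both available readings can mislead. If dropout differs by arm and heavier users leave more often, the comparison and path a shift toward the arm with more dropout. At 25% to 40% vs 15%, false-positive rates are about 20–75% (summed) or 11–50% (completers). Percent of assessed days gives about 5–9% in most runs, and up to 18% where use falls steeply.

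These sizes rest on assumed dropout rates and an assumed link between use and leaving. The documents do not show that XR-NTX will have more dropout or will appear to use fewer opioids; at pilot use rates the bias shrinks the gap and does not reverse it. This is a secondary outcome for which Section 17.9.1 disclaims Type I error control, and the primary analysis is unaffected. It should still be corrected, since a better measure is available from data already collected.

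**What to change.** 1. In Sections 5.2, 8.2, 17.3 and 17.9, define 3a as the percentage of TLFB-assessed days from randomization to week 24 with opioid use, and state how participants with no assessed days are handled.
2. In any count model under Section 17.9.1, use log(days assessed) as the offset.
3. Use the same variable as the mediator.
4. In Section 14.3, state that follow-up TLFB covers the time since the last completed TLFB.
5. Report days assessed by arm beside the result.
6. Add a sensitivity analysis scoring unassessed days as use days.

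The cost is SAP wording and one derived variable; no new data are needed. Percentages are imprecise for participants with short follow-up, and some bias remains if use changes over time or after dropout. The sensitivity analysis overshoots the other way: with dropout unrelated to use and 40% vs 20%, it was falsely significant in 54% of runs, against the arm with more dropout. Read it as a bound in that direction, not as a replacement estimate.

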5.2 Secondary Objectives

Secondary Specific Aims: Secondary aims compare the effectiveness of XR-NTX versus TAU in 1) other HIV outcomes (VACS Index, CD4 count), 2) engagement in HIV care (receipt of ART, ART adherence, retention in HIV care, HIV risk behaviors), and 3) ART adherence as mediated by number of opioid use days at 24 weeks. An additional secondary aim assesses barriers and facilitators of implementing XR-NTX for retaining patients in HIV primary care.

1) Secondary HIV Outcomes

- a. Change in VACS Index at 24 weeks, compared with randomization.
- b. Change in CD4 count at 24 weeks, compared with randomization.

2) Engagement in HIV Care:

- a. Proportion of participants prescribed ART within 24 weeks following randomization.
- b. Proportion of participants taking 100% of prescribed ART doses in the past month at 24 weeks for those prescribed ART at any point during the 24 week trial.
- c. Retention in HIV Care: Proportion of participants with at least 1 HIV primary care visit in the past 12 weeks, measured at week 24.
- d. HIV Risk Behaviors, as measured by the RAB at week 24.
- e. Quality of life as measured by EQ-5D at week 24, compared to baseline.

3) ART Adherence Mediation Variables:

- a. Number of days of opioid use since baseline, measured by Timeline Follow Back (TLFB) at 24 weeks.
- b. Past 30 day opioid abstinence (by Addiction Severity Index (ASI)-lite self-report, Timeline Follow Back (TLFB) and urine drug screen (UDS) confirmation at 24 weeks).

4) Assess barriers and facilitators of XR-NTX implementation to improve retention in HIV primary care:

Qualitative interviews with participants, providers, and staff to document the HIV primary care treatment environment and describe XR-NTX formative implementation strategies, challenges, and best practices.

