9.1.3 Screening and Enrollment Procedures (1-4 weeks duration)

Once a person has completed the Pre-Screening Interview process and meets basic eligibility criteria, they will either be asked to stay for the Screening Visit or scheduled to come back for the visit (based on staff and candidate's availability). It is expected that the screening and enrollment phase will take approximately 1-4 weeks; however, participants will have 60 days from the date of consent to complete screening and be randomized before being considered a screen failure.

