9.1.9 Randomization

The timing of randomization will follow shortly after baseline assessments and final confirmation of eligibility. Participants will be encouraged to initiate treatment within 28 days of randomization. If a participant is unable to initiate treatment within 28 days, he or she may initiate XR-NTX study drug at any time until week 20 and may initiate TAU at any time during the trial. Initiation of assigned treatment will be tracked.

Participants will be randomized in a 1:1 fashion to either office-based XR-NTX or TAU using a permuted block design with randomly-sized blocks. Randomization will be stratified only by site. Participants who meet DSM-5 criteria for both opioid and alcohol use disorder (16% of CTN-0055 CHOICES pilot study participants) will be included, in addition to participants with OUD, alone.

Concomitant alcohol use disorder will be considered as a potential covariate [31], [127, 128]. Participants need not be abstinent from opioids at the time of randomization.

The randomization procedure will be conducted in a centralized process through the Data and Statistics Center (DSC). Specifically, randomization schedules will be created by the study statistician for each site. The randomization schedules will be of a randomized-block nature to ensure relative equality of assignment across condition across the recruitment period and to prevent the potential for study staff guessing the next assignment, which is heightened when a fixed block-size is used. After the baseline assessment is successfully completed, a designated site study staff member will perform the randomization. Randomization for each participant is done over the internet using the Enrollment Module in Advantage eClinical.

The DSC statistician will review the randomization data on a regular basis to ensure that the scheme is being implemented according to plan. If a participant drops out of the study at any point after randomization, the randomization slot will not be re-allocated to a new participant due to the intent-to-treat nature of the study.

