Concise Health Risk Tracking – Self Report			X		X	X	X	X	X	X	X	X		
Concise Health Risk Tracking – Clinician Rated														X
DSM-5 Substance Use Disorders		X												
Urine Drug Screen		X			X*	X*	X	X	X	X	X	X	X	
HIV Care Utilization			X										X	X
Buprenorphine and Methadone Chart Abstraction							X	X	X	X	X	X	X	
Quality of Life, from PhenX			X											
Quality of Life, from EQ-5D			X									X	X	

Assessment/Activity	Pre-Screening	Screening	Baseline	Randomization ^{^A}	Treatment Initiation	Safety Visit	Week 4	Week 8	Week 12	Week 16	Week 20	Week 24	End of Study (#Week 24)	As Needed
Risk Assessment Battery			X				X	X	X	X	X	X	X	
Tobacco Use History and Substance Use History, from PhenX			X									X	X	
Timeline Follow Back			X		X		X	X	X	X	X	X	X	
Treatment Plan				X			X	X	X	X	X	X	X	
Treatment Initiation***													X	X
XR-NTX Non-Initiation*														X
Treatment Satisfaction Survey													X	X
Treatment Services Review			X		X		X	X	X	X	X	X	X	
VACS Index				X									X	X
Visual Analog Scale			X				X	X	X	X	X	X	X	
PHQ-9 Depression Symptoms			X						X			X	X	
Suicidal Risk														X
Criminal Justice			X						X			X	X	
Participant Treatment Preference			X											

* Only for participants randomized to the XR-NTX arm.

**At randomization, HCV PCR confirmation is required when HCV ab is positive. At 24 weeks, collect HCV ab if participant tested HCV ab negative at randomization or if HCV ab result was not obtained at randomization. At 24 weeks, collect HCV PCR confirmation if: HCV antibody is positive at randomization, but HCV PCR was not obtained at randomization or HCV antibody was negative at randomization, but HCV antibody is positive at Week 24.

*** Only for participants randomized to TAU arm.

[‡] Height and weight only for BMI calculations.

⁺⁺ Not captured in eClinical.

[^]Urine pregnancy test required for XR-NTX group only; remainder of Pregnancy and Birth Control Assessment required for all participants.

^{^A}Assessments performed at randomization correspond with Week 0 requirements in the eClinical system.

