17.3 Secondary Outcome Measures

1) Secondary HIV outcomes variables:

- a. VACS Index. Change in VACS Index score at 24 weeks compared with randomization (continuous; laboratory assays and demographics).
- b. CD4 Count. Change in CD4 count at 24 weeks following treatment initiation compared with randomization (count; laboratory assay).

2) Engagement in HIV Care Variables:

- a. ART prescribed. Proportion of participants prescribed ART within 24 weeks following randomization (binary; medical record abstraction).
- b. ART Adherence. Proportion of participants taking 100% of prescribed ART doses in the past month at 24 weeks for those prescribed ART at any point during the 24 week trial (binary; self-reported medication adherence measure).
- c. Retention in HIV Care: Proportion of participants with at least 1 HIV primary care visit in the past 12 weeks, measured at week 24. Adherence to HIV clinic visits in the year after ART initiation predicts HIV disease progression and death [164] (binary; medical record abstraction).
- d. HIV Risk Behaviors. Past 30 day injection drug use, unprotected sex, multiple sexual partners as measured by the RAB at week 24 (binary; self-report).
- e. Quality of life. Past 30 day health-related quality of life as measured by EQ-5D at week 24.

3) ART Adherence Mediation Variables:

- a. Days of Opioid Use. Number of days of opioid use since baseline, measured by Timeline Followback at 24 weeks (count; self-report).
- b. Opioid Abstinence. Past 30 day opioid abstinence (by Addiction Severity Index (ASI)-lite self-report, Time-Line Follow-Back (TLFB) and urine drug screen (UDS) confirmation) in the final 30 days of the 24 week trial (binary; self-report + UDS).

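### Opioid-use days are counted from the baseline visit, not randomization, so days before assignment can enter outcome 3a and the aim 3 mediator; the effect is small and the remedy free

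*Combined protocol and SAP*

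**What the plan says.** Section 8.2 defines the outcome as "Number of days of opioid use since baseline, as measured by Timeline Follow Back (TLFB) at 24 weeks". Section 17.3 has "Number of days of opioid use since baseline, measured by Timeline Followback at 24 weeks (count; self-report", Section 5.2 uses the same starting point, and the analysis text in Section 17.9 item 3a has "Number of days of opioid use between baseline and 24 weeks, measured by TLFB (count; self-report". Section 5.2 also gives opioid-use days the role of mediator: "ART adherence as mediated by number of opioid use days at 24 weeks".

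Baseline and randomization are separate columns in the Section 10.1 schedule, whose footnote says "Assessments performed at randomization correspond with Week 0 requirements in the eClinical system". On the order of events, Section 9.1.9 states: "The timing of randomization will follow shortly after baseline assessments and final confirmation of eligibility". The only numerical limit covers the whole screening phase; Section 9.1.3 says "participants will have 60 days from the date of consent to complete screening and be randomized", with 1 to 4 weeks expected.

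On data capture, Section 14.3 says "Baseline TLFB assesses use in the 30 days prior to informed consent through to the date of the baseline visit". Later TLFBs record use day by day over a specified period, with the time since the previous visit given as an example. The schedule has a TLFB at baseline, treatment initiation and Weeks 4 to 24, and none at randomization.

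**The concern.** Assignment cannot affect a day that precedes it. If the count opens at the baseline visit, each participant's total is a post-randomization part plus a pre-randomization part whose length depends on how quickly that participant was randomized. The second part carries no information on treatment.

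Three things are at stake:

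- Any ratio of counts moves toward 1. Section 17.9.1 names Poisson, zero-inflated Poisson and negative binomial models, which with their usual log link estimate ratios, and it states no offset for unequal windows. A participant who stops using opioids from randomization onward but used during the gap is also scored as non-zero.
- The extra days add variance, which weakens the rank-sum test and the treatment-to-mediator path.
- Part of the mediator becomes pre-treatment severity. That cannot lie on the causal path from treatment, but it may be related to adherence.

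The starting point also departs from the rest of the plan. The primary endpoint (Section 17.2) is dated from randomization, and the VACS Index and CD4 changes (Section 8.2) are measured against it.

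**Working it through.** **The plan's own figure.** No power is stated for the comparison of opioid-use days. Section 17.9 claims over 80% power for mediation at standardized paths a = b = 0.164, or about 2.7% shared variance. Check: 0.164² = 0.0269. A simulation of the bias-corrected bootstrap interval (N = 350 assumed, since that paragraph gives no N; 1:1 arms, no direct effect, 1,000 trials of 1,000 resamples) gives 81.6%, with Monte Carlo standard error √(0.816 × 0.184 / 1000) ≈ 1.2 points. The stated figures reproduce.

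**Inputs for the window.** Pilot days of opioid use per 30 (Section 4.3) went from 19 to 10 for TAU (n = 12) and from 18 to 13 for XR-NTX (n = 10). Follow-up is 24 × 7 = 168 days, with 175 per arm (Section 17.1). The gap g is not stated, so a range is used.

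**Mean counts.**
- Pre-randomization rate: (19 + 18)/2 ÷ 30 = 0.617 days per gap day.
- From randomization: TAU 168 × 10/30 = 56.0; XR-NTX 168 × 13/30 = 72.8; difference 16.8; ratio 72.8/56.0 = 1.30.
- From baseline: add 0.617 × g to both arms.

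**Power.** Take an effect with 80% power when counting starts at randomization: d = (1.960 + 0.842) × √(2/175) = 0.30. With a fixed gap, equal between-person SD of the daily use rate before and after randomization (it cancels; 0.35 was used) and correlation ρ between the two, the standardized effect is multiplied by k = 168 / √(168² + g² + 2ρ × 168 × g). Power is then about Φ(2.80k − 1.96). The range below is for ρ from 0.7 to 0.

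| Gap g (days) | Days added | TAU mean | XR-NTX mean | Difference | Ratio | Power |
|---|---|---|---|---|---|---|
| 0 | 0 | 56.0 | 72.8 | 16.8 | 1.300 | 80% |
| 1 | 0.6 | 56.6 | 73.4 | 16.8 | 1.297 | 79.7–80.0% |
| 7 | 4.3 | 60.3 | 77.1 | 16.8 | 1.279 | 77.6–79.9% |
| 14 | 8.6 | 64.6 | 81.4 | 16.8 | 1.260 | 75.2–79.8% |
| 28 | 17.3 | 73.3 | 90.1 | 16.8 | 1.229 | 70.3–78.9% |

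Worked case, g = 7 and ρ = 0.7: k = 168 / √(28224 + 49 + 1646.4) = 168/172.97 = 0.971; power = Φ(2.72 − 1.96) = 77.6%.

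This is a normal approximation on means, so it only approximates the planned rank-sum test. It omits the further variance that arises when the gap differs between participants.

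**Mediation.** At ρ = 0.5, k is 0.979 for 7 days and 0.915 for 28 days. Multiplying path a by 0.98 and 0.92, with path b held fixed, gives simulated power of 80.6% and 79.4% against 81.6%. Both drops are about the size of the Monte Carlo error. The simulation does not capture any change in path b caused by pre-treatment severity entering the mediator.

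**The case against.** The strongest reply is that the wording is loose but harmless.

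- **Baseline is used loosely.** Item 3a also counts urine screens from baseline, although the schedule collects them at screening and not at the baseline visit. The baseline viral load likewise comes from screening or from records. The authors may therefore mean Week 0. That is possible, but the text does not settle it, and it uses the two terms distinctly elsewhere. A programmer needs one start date.
- **The gap is probably short.** Section 9.1.9 points that way, and same-day randomization makes the effect nil. This stands. A reader might take the 1 to 4 weeks or the 60 days in Section 9.1.3 as the likely gap, but both run from consent across the whole phase and only bound it from above.
- **Gap days may not be collected.** If randomization counts as the last visit, the next TLFB would look back only that far. Section 14.3 gives that look-back as an example, not a rule. On this reading the count has a hole at its start instead of extra days, so the definition and the data still disagree.
- **Other analyses do not depend on the start date.** The ASI-Lite count over the last 30 days and outcome 3b do not, and Section 17.9.1 allows adjustment for severity of opioid use disorder. This limits the damage but does not correct outcome 3a or the mediator.

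A reader might also infer that the arm difference itself is diluted or biased. It is not. Randomization balances pre-assignment days in expectation, and the difference stays at 16.8 days for every gap.

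**Conclusion.** The point holds as a minor flaw of definition. As written, the window opens before assignment, so whenever the gap exceeds zero the rule admits days that treatment cannot influence into both the outcome and the mediator. The absolute arm difference remains unbiased. The cost is a count inflated by about 0.6 days per gap day, a ratio moved toward 1 (1.30 to about 1.28 at 7 days and 1.26 at 14 days), a loss of about 0 to 2.5 power points at 7 days, and a mediator that partly measures pre-treatment severity. The loss becomes material only with gaps of several weeks, which the documents do not suggest are typical.

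The sizes rest on pilot rates from 12 and 10 participants held constant over 168 days, an assumed gap, and assumed variances and correlations. Nothing here touches the primary endpoint. The outcome is secondary, and Section 17.9.1 says overall Type I error is not controlled for these analyses.

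**What to change.** In Sections 5.2, 8.2, 17.3 and 17.9 item 3a, define the count as TLFB opioid-use days from the day after the randomization date to the Week 24 assessment, and use the same definition for the mediator. Treat TLFB days up to and including the randomization date as baseline data, available as a covariate. State in Section 14.3 that the first post-baseline TLFB covers the calendar from the baseline visit, so that the cut can be made by date. Leave the end of the window as the plan has it.

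The cost is the wording in these places and one date filter in the programming. TLFB already records use by day, so no visit or instrument is added. The change should be made before database lock, so that the start date is not chosen after the data are seen.
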